10.3.3 Safety and Reactogenicity

The analysis population will be all randomised participants who received at least one study vaccine. Counts and percentages of each local and systemic solicited adverse reaction from diary cards, and all unsolicited AEs and SAEs will be presented by schedules of vaccine received.

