Recruitment window (wk)	Total n=200 for each vaccine for cohort 1 + cohort 2	Day 0	Short 4-6 wk	Long 8 wk-12wks*
24 0/7 – 27 6/7		Vaccine A	- **	Vaccine A
		Vaccine A	Vaccine A	- **
		Vaccine B	- **	Vaccine B
		Vaccine B	Vaccine B	- **
		Vaccine C	- **	Vaccine C
		Vaccine C	Vaccine C	- **

* “Long” dose must be given by 36 weeks’ gestation

** dTaP/IPV should be given by 32 weeks’ gestation with an interval of at least 1 week before / after receipt of COVID-19 vaccine

Table 3. Cohort 3.

Recruitment window (wk)	Total n=100	Day 0	Post delivery (4-12 weeks but given after delivery)*
28 0/7 – 34 0/7		Vaccine A	Vaccine A
		Vaccine B	Vaccine B
		Vaccine C	Vaccine C

* Booster dose should be given as soon as possible after delivery

** if require dTaP/IPV, it should be given by 32 weeks' gestation and with an interval of at least 1 week before / after receipt of COVID-19 vaccine

Table 4. Cohort 4.

Recruitment window (wk)	Total n= 100	Boost dose <26 weeks	Boost dose ≥26 weeks
13 0/7 – 34 0/7		Vaccine A/B/C/D*	Vaccine A/B/C/D*

*Same vaccine as given pre-pregnancy / first trimester (0 0/7 – 12 6/7 gestational weeks)

** if require dTaP/IPV, it should be given by 32 weeks' gestation and with an interval of at least 1 week before / after receipt of COVID-19 vaccine

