3.5 Secondary endpoints/outcomes

Maternal

- Pregnancy outcomes from Visit 1 up to 6 weeks after delivery. These include live birth with congenital anomalies, miscarriage, fetal death/still birth (antepartum or intrapartum), mode of delivery, elective/therapeutic termination.
- Occurrence of serious adverse events (SAEs), AEs leading to study withdrawal, and MAAEs from Visit 1 (Day 0) up to 6 weeks / 6 months after delivery

- AEFI from Visit 1 up to 6 weeks after delivery. These include but are not limited to maternal death, hypertensive disorders of pregnancy (gestational hypertension, pre-eclampsia, pre-eclampsia with severe features including eclampsia), antenatal bleeding (morbidly adherent placenta, placental abruption, caesarean scar pregnancy, uterine rupture), postpartum haemorrhage, fetal growth restriction, gestational diabetes mellitus, non-reassuring fetal status, pathways to preterm birth (premature preterm rupture of membranes, preterm labour, iatrogenic preterm birth), chorioamnionitis, oligohydramnios, polyhydramnios, gestational liver disease (intrahepatic cholestasis of pregnancy, acute fatty liver of pregnancy), maternal sepsis.
- SARS-COV-2 IgG-specific antibody concentrations, (and neutralizing antibody titres and cellular immune responses in subsets) measured on blood samples collected from vaccinated maternal subjects at Day 0 (before vaccination), Day 28-42, Day 56-84, Day 84-112, Day 112-140, at delivery, between 4 weeks and 12 weeks, and at 12 months after delivery

Infant

- From birth through 6 weeks after birth, occurrences of SAEs, AEs leading to study withdrawal, and MAAEs
- Occurrence of neonatal AEs of special interest (up to 6 weeks after birth). These include but are not limited to small for gestational age, low birth weight including very low birth weight, neonatal encephalopathy, congenital microcephaly (postnatally or prenatally diagnosed), congenital anomalies (major external structural defects, internal structural defects, functional defects), neonatal death (in a preterm live birth or in a term live birth), neonatal infections (blood stream infections, meningitis, respiratory infection), respiratory distress in the neonate, preterm birth, failure to thrive, large for gestational age, macrosomia
- Developmental status at 12 months of age

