Clinically significant pregnancy-related conditions according to medical judgement

Clinically significant acute illness at the time of vaccination

Fever (body temperature $\geq 38.0^{\circ}\text{C}$ [100.4°F]) within 24 hours prior to the planned vaccination

Symptomatic participants

Participants will be counselled at enrolment that should they receive a positive SARS-CoV-2 test (e.g. an antigen detection or nucleic acid amplification test, for example, via test and trace or occupational health services) they should contact the trial team on receipt of the positive result.

Once the participant has conveyed their result to the study team, and the study team confirm an appropriate test has been used (via verbal discussion with participant as to how testing was obtained). Confirmatory documentation may be sought from the participant (such as a forwarded email or a picture of a lateral flow assay result, but this is not essential). Cases of positive COVID-19 maternal infection will be noted.

Symptomatic infants will also receive an appropriate SARS-CoV-2 test and if positive an appointment will be arranged to review the participant at the relevant study site. At this visit blood samples for safety (FBC, Biochemistry, CRP and others if deemed clinically relevant) and immunology (PBMCs and serum for cellular and humoral immune responses) will be obtained. Vital signs and other clinical data will be recorded.

Participants (mothers/infants) will also be provided with a symptom diary to complete both solicited and unsolicited symptoms for at least 7 days and until symptom resolution (excepting persistent cough and anosmia/dysgeusia as these are recognised to be able to continue for extended periods). Additional visits on this pathway may be arranged at the clinical discretion of the investigator.

Lost to follow up

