7.3 The randomisation scheme

7.3.1 Method of implementing the randomisation/allocation sequence

For the main study (cohort 1 and cohort 2), computer generated randomisation lists will be prepared by the study statistician. Participants will be randomised 1:1:1:1:1 for each of the vaccine groups (Pfizer / Moderna / Novavax) at "short" and "long" prime-boost intervals, using block randomisation. Random block sizes of 6 or 12 will be used. The randomisation will be stratified by the study cohort and study sites.

For the sub-study of cohort 3, participants will be randomised 1:1:1 to the study vaccines (Pfizer / Moderna / Novavax) using block randomisation. Random block sizes of 3 or 6 will be used, and the randomisation will be stratified by study sites. The sub-study of cohort 4 will be an open label study, women primed with a COVID-19 vaccine will be randomised to a boost vaccine (of the same type) before or after 26 weeks of gestational age on a 1:1 basis. Random block sizes of 2 or 4 will be used and stratified by study sites.

The study design is "adaptive" in that new COVID-19 vaccines may be included as soon as they are licensed. Randomisation will be adjusted accordingly. The allocation ratio will adaptively evolve over the course of the trial and will be fully described in the Interim Analysis.

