7.10 Withdrawal criteria

In consenting to the trial, participants are consenting to trial treatments, trial follow up and data collection. However, an individual participant may stop treatment early or be stopped early for any one of the following reasons:

- Having received vaccination outside of the study after randomisation, but before vaccination by the study team
- Any change in participant’s condition that in the investigator’s opinion justifies the discontinuation of follow up
- Withdrawal of consent by the participant

As participation in the trial is entirely voluntary, the participant may choose to discontinue treatment at any time without penalties or loss of benefits to which they may be entitled. Although not obliged to give a reason for discontinuing their trial treatment/ protocol inclusion a reasonable effort should be made to establish this reason, whilst remaining fully respectful of the participant's rights.

Participants who discontinue protocol treatment, for any of the above reasons, should remain in the trial for the purpose of follow up and data analysis.

However, if the participant confirms they do not wish to participate in the scheduled follow up data collection visits, then data that has already been collected should be kept and analysed according to the ITT principle, unless the participant specifically requests otherwise.

Participants who stop the trial follow up after receiving vaccination will not be replaced. Participants who withdraw prior to vaccination may be replaced.

If there is a change in the national recommendations or a safety signal is demonstrated the trial management group would consider if the study should be prematurely stopped.

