Ongoing global studies have so far found that pregnant women are more likely to develop severe COVID-19 disease compared to non-pregnant women of the same age. Pregnant women who develop COVID-19 symptoms are two to three times more likely to have their baby early. Pregnant women with COVID-19 also have a higher mortality rate than pregnant women without COVID-19. For these reasons, the current UK national guidance on immunisation is that COVID-19 vaccination should be offered to pregnant women at the same time as the rest of the population. However, further pregnancy-specific research is needed on COVID-19 vaccines.

The trial will compare vaccines that are currently being used for the UK vaccination programme, as well as new vaccines as they are approved. Low-risk pregnant women aged 18 - 45 years and between 13-34 weeks gestation can be considered for enrolment into the study.

Once they have given their consent, participants who have not yet received any COVID-19 vaccines will be randomised to receive two doses in a short-time interval (4-6 weeks) or a long-time interval (8-12 weeks). For some participants this means they will receive their second dose after delivery. Participants will be blinded to the vaccine they receive. The majority of participants will also be blinded to the interval between doses by incorporating the pertussis (whooping cough) vaccine into the trial schedule.

Alternatively, for those who have already received their first dose of a COVID-19 vaccine prior to pregnancy, participants will receive a second dose of the same COVID-19 vaccine they have previously received.

Participants will be followed up until one year after delivery. Blood samples will be taken from participants throughout the study. A cord blood sample will be taken after delivery. This is taken from the umbilical cord after the baby has been born and the cord has been cut; this is not a sample taken from the baby. A baby blood sample will then be taken at either 4-6 weeks or 10-12 weeks of age. Participants will be asked to complete a symptom diary and any significant medical events will be investigated. For a sub-group of participants breast milk samples will also be collected.

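### Section 10.3.3 groups SAEs and unsolicited AEs by schedule received, which is settled only at dose 2, so the short-versus-long safety description can be biased

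*Protocol*

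**What the plan says.** Section 10.3.3 is the protocol's rule for analysing safety. It sets the population, "The analysis population will be all randomised participants who received at least one study vaccine", and the grouping: "all unsolicited AEs and SAEs will be presented by schedules of vaccine received". It names solicited reactions, unsolicited AEs and SAEs. It does not name MAAEs, AESIs or pregnancy outcomes, and it does not say where a woman with one dose, or with a late second dose, is counted.

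The surrounding design is as follows.

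- Cohorts 1 and 2 are randomised to vaccine and interval, with dose 1 at Visit 1 (sections 7 and 7.3.1). Dose 2 follows at 4-6 weeks (short) or 8-12 weeks (long) (section 2, Tables 1 and 2).
- In cohort 1 the long dose must be given by 32 weeks' gestation. In cohort 2 the long "dose must be given by 36 weeks".
- SAEs and MAAEs count from Day 0 (sections 3.5 and 3.7). The secondary endpoints include "Pregnancy outcomes from Visit 1 up to 6 weeks after delivery".
- The contraindications to vaccination in section 7 include "Clinically significant pregnancy-related conditions according to medical judgement".
- Baseline data are summarised by study arm (10.3.1), and the primary outcome is compared between interval arms under modified intention to treat (10.3.2).

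**The concern.** The two interval arms receive the same first dose and differ only in when the second falls. A grouping that depends on the second dose is settled after randomisation, by events that include the safety outcomes themselves. To qualify as having received the long schedule a woman must remain eligible for vaccination for 8-12 weeks; for the short schedule, 4-6 weeks. Events during that wait are already being counted as SAEs.

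At stake is the description of harm by interval. The long interval's immune response would be judged on randomised arms and its SAEs on groups formed later.

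**Working it through.** The protocol gives no safety calculation to reproduce. Its only calculation (section 10.1, 75 evaluable women per arm) concerns IgG and plays no part here.

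**1. Cohort 2, from the protocol's own dates.** Enrolment opens at 24 0/7 weeks.

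- Earliest short second dose: 24 + 4 = 28 0/7 weeks.
- Earliest long second dose: 24 + 8 = 32 0/7 weeks.

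A birth at 28-31 weeks can follow a completed short schedule but not a completed long one. This takes dose 2 as antenatal, as the 36-week limit and the cohort 1 and 2 visit schedule imply. Preterm birth is a listed neonatal event of special interest. No event rate is needed for this step.

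**2. Length of the wait.** At mid-interval it is 10 against 5 weeks, a ratio of 2. The extremes are 8/6 = 1.3 and 12/4 = 3.0.

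**3. Share of the event window before dose 2.** Assumptions: constant event rate from Day 0 to 6 weeks after birth at 40 weeks; enrolment gestation g uniform over 13-24 weeks (cohort 1) or 24-28 weeks (cohort 2); dose 2 uniform within its window, subject to the 32- or 36-week limit. The window is 46 - g weeks.

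- Cohort 1 short: 5 × ln(33/22)/11 = 0.184.
- Cohort 1 long: {10 × ln(33/26) + 0.5 × [4 - 6 × ln(26/22)]}/11 = 0.353.
- Cohort 2 short: 5 × ln(22/18)/4 = 0.251.
- Cohort 2 long: 0.125 × [4 - 2 × ln(22/18)] = 0.450.

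**4. Apparent ratio when the true ratio is 1.** Let f be the share of pre-dose-2 events that stop dose 2, and suppose those women are set apart. Then ratio = (1 - f × long share)/(1 - f × short share).

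| f | Cohort 1 | Cohort 2 |
|---|---|---|
| 0.25 | 0.912/0.954 = 0.96 | 0.888/0.937 = 0.95 |
| 0.50 | 0.824/0.908 = 0.91 | 0.775/0.875 = 0.89 |
| 1.00 | 0.647/0.816 = 0.79 | 0.550/0.749 = 0.73 |

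**5. A second construction, removing women from the denominator too.** Assume a 10% event risk over 26 weeks, waits of 5 and 10 weeks, and half of pre-dose-2 events stopping dose 2. The weekly hazard is -ln(0.9)/26 = 0.00405. Events before dose 2 are 2.01 and 3.97 per 100, so 1.00 and 1.99 per 100 are removed. The observed risks are (10 - 1.00)/(100 - 1.00) = 9.09% short and (10 - 1.99)/(100 - 1.99) = 8.18% long, a ratio of 0.90. With a tenth or all such events stopping dose 2 it is 0.98 or 0.77.

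**6. The opposite direction.** Suppose 10 of 100 women have an event in each arm, and two short-arm women with events have dose 2 deferred into the long window and are counted as long. Short becomes 8/98 = 8.2% and long 12/102 = 11.8%, a ratio of 1.44.

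**The case against.** The strongest reply is that section 10.3.3 never removes anyone from the long group. All women with at least one dose stay in the safety population, and elsewhere in the protocol the word schedule denotes the assigned regimen. A one-dose woman assigned to long could be tabulated as long, with the detail left to the statistical analysis plan. This is right as far as it goes. A reader might infer that such women leave the safety analysis; the text does not say so. But the protocol does fix the grouping as what was received. Keeping a one-dose woman in her assigned column is grouping by randomisation, which the sentence does not prescribe.

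Other points that stand:

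- Safety is descriptive (counts and percentages). No between-interval safety test is planned, and superiority concerns IgG only.
- A safety table by treatment received is a common convention, and it suits solicited reactions.
- Section 6.4 allows out-of-window vaccination after acute illness or fever, so reversal is possible. It is limited: moving from 6 to 8 weeks takes at least a 2-week delay, and delivery or loss is not a deferral.
- The value of f has no source in the protocol, and f = 1 is implausible for general adverse events. Events clustered around delivery mostly follow dose 2 in both arms, so a constant rate overstates the pre-dose-2 shares. Section 3.5 also mentions 6 months after delivery for SAEs; that longer window would bring the ratios nearer 1.
- Removing women from the denominator matters when events are common: at an assumed 50% risk and f = 0.5, cohort 1 moves from 0.91 to about 0.95.

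A reader might also see a conflict with section 7.10, where "data that has already been collected should be kept and analysed according to the ITT principle". That sentence concerns women who decline further follow-up visits. It does not set the safety grouping, so no direct contradiction follows.

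**Conclusion.** The concern holds as a badly chosen grouping rule, not as a demonstrated understatement of harm. Read literally, grouping by schedule received makes the short-versus-long description of SAEs depend on events after randomisation, with about twice the qualifying time in the long arm. The cohort 2 result, no birth before 32 weeks under a received long schedule, follows from the protocol's dates and the antenatal timing of dose 2.

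The tempting stronger statement, that harms of the long interval are understated, is not supported: size and sign depend on an unstated classification of one-dose and deferred women. If one-dose women are set apart, the bias most likely favours the long interval, illustratively 0.73-0.96 for f from 25% to 100% under a constant rate. If deferred short-arm women are counted as long, it can go the other way.

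For pregnancy outcomes, MAAEs and AESIs the point holds only if they are tabulated the same way. The 7-day and 30-day windows after dose 1 are barely affected, because the earliest second dose is on Day 28 and those windows close almost wholly before it in both arms.

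**What to change.** In section 10.3.3, state that SAEs and the other events counted from Day 0 (MAAEs, AESIs, pregnancy and infant outcomes) are tabulated by randomised interval within vaccine, among all randomised women who received dose 1. Keep solicited reactions and post-dose unsolicited AEs per dose actually given. Show as-received tables as supplementary, with footnotes for women who had one dose, an out-of-window dose or the wrong product. The statistical analysis plan should carry the same wording.

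No new data are needed. The cost is a short text change and one extra set of tables.

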10.4 Interim analysis and criteria for the premature termination of the trial

The interim analysis on immunogenicity will be carried out when the primary endpoint of anti-spike IgG data at delivery become available, while the interim analysis on reactogenicity will be conducted when the 7-day diary data become available for both the “short” and “long” prime-boost interval arms. The analysis will be carried out once the data is cleaned and the Study Analysis Plan is signed off. There will be no stopping rule for this interim analysis and the analysis will not affect the continuation of the trial.

10.8 Procedure(s) to account for missing or spurious data

The level and pattern of the missing data in the baseline variables and outcomes will be reported. The potential causes of any missing data will be investigated and documented as far as possible. Any missing data will be dealt with using methods appropriate to the conjectured missing mechanism and level of missing.

10.9 Economic evaluation

N/A

11 Data Management

11.1 Data collection tools and source document identification

The Chief Investigator will be responsible for all data that accrues from the study.

All study data including participant diary will be recorded directly into an EDC system (REDCap) or onto a paper source document for later entry into EDC if direct entry is not available. This includes safety, laboratory and outcome data. Any additional information that needs recording, but is not relevant for the eCRF (e.g signed consent forms) will be recorded on separate paper source documents. All documents will be stored safely and securely in confidential conditions. The EDC online data is stored on University of Oxford servers.

All participant reported adverse event data (both solicited & unsolicited) will be entered onto electronic diary cards (e-diaries) for a maximum of 28 days following administration of the IMP. The eDiary provides a full audit trail of edits and will be reviewed at time-points as indicated in the schedule of events. Any adverse event continuing beyond the period of the diary will be copied into the eCRF as required for safety review.

The participants will be identified by a unique trial specific number and code in any database. The name and any other identifying detail will NOT be included in any trial data electronic file, with the exception of the electronic diaries, for which consent will be obtained to store the participant email address for quality control purposes. Only site research staff and sponsor data managers have access to view the email address.

The EDC system (CRF data) uses a relational database (MySQL/ PostgreSQL) via a secure web interface with data checks applied during data entry to ensure data quality. The database includes a complete suite of features which are compliant with GCP, EU and UK regulations and Sponsor security policies, including a full audit trail, user-based privileges, and integration with the institutional LDAP server. The MySQL and PostgreSQL database and the webserver will both be housed on secure servers maintained by the University of Oxford IT personnel. The servers are in a physically secure location in Europe. Backups will be stored in accordance with the IT department schedule of daily, weekly, and monthly retained for one month, three months, and six months, respectively. The IT servers provide a stable, secure, well-maintained, and high capacity data storage environment. REDCap is a widely used, powerful, reliable, well-supported system. Access to the study's database will be restricted to members of the study team by username and password.

Source Data

Source Data and Case Report Forms (CRFs)

All protocol-required information will be collected in CRFs designed by the Investigator. All source documents will be filed in the participant file. Source documents are original documents, data, and records from which the participant CRF data are obtained. For this study, these will include, but are not limited to, volunteer consent form, blood results, GP response letters, laboratory records, diaries, medical records and correspondence. In the majority of cases, CRF entries will be considered source data as the CRF is the site of the original recording (i.e. there is no other written or electronic record of data). In this study this will include, but is not limited to medical history, medication records, vital signs, physical examination records, urine assessments, safety blood results, adverse event data and details of vaccinations. All source data and participant files will be stored securely.

To prevent withdrawal of a participant due to relocation, if there is a nearby participating site and with the consent of the participant, copies of relevant participant research records (such as ICF, paper source documents) will be transferred to the local site using secure email addresses such as nhs.net or by password protected sheets. The electronic research data stored on REDCap will also be transferred to the new site. The original records will be retained by the recruiting site.

